1.0 STATEMENT OF COMPLIANCE

This document is a clinical investigational plan for a human research study Sponsored by Merck Corporation. The study will be conducted in compliance with all stipulations of this protocol, ethical principles that have their origin in the

Declaration of Helsinki, the conditions of IRB/EC approval, applicable federal and local regulatory requirements, ISO-14155 and International Conference on Harmonization (ICH) E6 on Good Clinical Practice (GCP) guidance.

2.0 TABLE OF ABBREVIATIONS

Abbreviation	Meaning
OSA	Obstructive sleep apnea
GFR	Glomerular filtration rate
FDA	Food and Drug Administration
IRB	Institutional Review Board
PACU	Post Anesthesia Care Unit
AE	Adverse Event
SAE	Severe Adverse Event
SUSAR	Suspected Unexpected Serious Adverse Reaction
Hb	Hemoglobin
RRUMC	Ronald Reagan UCLA Medical Center
EMR	Electronic medical record
BMI	Body mass index

3.0 PROTOCOL SUMMARY

Sponsor	Merck & Co., Inc.
Protocol Title	A prospective digital quality improvement project to apply best clinical practices to patients at high risk of respiratory complications
Drugs	The following FDA cleared drugs will be used in this study: 
 • Sugammadex
Study Objectives	Primary Objective 
 1) Time to “fitness for discharge” from the recovery room, as noted by the time the anesthesiologist places the discharge order, before and after intervention.

	
2) Incidence of hypoxemia in the PACU before and after intervention as defined by documentation oxygen saturation below 90%
 
Secondary Objectives
 
 1) Performance of identified best practices before and after intervention. 2) Incidence of hypoxemia in the PACU before and after intervention as defined by documentation of oxygen saturation below 95% 3) The duration of supplemental oxygen needed by high risk patients before and after intervention 4) Postoperative reintubation rate 5) Unplanned upgrade of care (defined as patients who are sent to the ICU after being admitted to a regular ward)
Study Design	Historical prospective comparative effectiveness trial
Study Phases	
Retrospective Data Analysis
 
Perform a retrospective analysis on data contained in our data warehouse on the incidence of respiratory dysfunction in the post-operative care unit (PACU) before and after the introduction of sugammadex into clinical practice.
 
Respiratory depression pathway implementation
 
Develop and implement a clinical best practice pathway designed to prevent postoperative respiratory complications in higher risk patients (such as those with OSA or preexisting respiratory disease) using education and clinical decision support in patients.

Sample Size	~13,000 retrospective and ~6,500 prospective
Clinical Sites	Ronald Reagan UCLA Medical Center, UCLA Santa Monica Hospital
Study Population	RRUMC or UCLA Santa Monica patients aged 18 and older who had a general anesthetic with either rocuronium or vecuronium.
Inclusion Criteria	
One or more:
 
 • Obstructive or restrictive lung disease in EMR • OSA • Preoperative O2 sat <95% (avg/median of 12 hours before surgery) • BMI > 40 • Acute respiratory infection within 1 month prior to surgery

[figure not shown]
	
 • Previous history of airway pathology 
Two or more:
 
 • BMI>35 • Multiple intubation attempts • Surgical duration >2 hours • Upper abdominal surgery, intrathoracic surgery, or airway/head and neck surgery • Most recent Hb (within 6 months only) <10
Exclusion Criteria	
 • Pregnant or lactating (or gave birth within last year) • Age<18 • Documentation of allergy or previous reaction to sugammadex • GFR<30 • Neuromuscular disease (ICD codes) • Remain intubated/tach post-op • Surgery at a site other than RR OR or SM OR
Study Endpoints	
 1) PACU Discharge Time (primary endpoint) 2) Incidence of oxygen saturation <90 3) Incidence of oxygen saturation <95% 4) Duration of supplemental oxygen use in PACU 5) Reintubation rate 6) Unplanned Upgrade of Care
Safety Evaluation	All adverse events reported by participating clinicians between enrollment and 48 hours after drug administration will be tabulated.
Study Procedures	
 • Retrospective analysis: PDW data extracted and analyzed to determine incidence of respiratory depression, changes in slope at time of sugammadex introduction, and associations between reversal practices and time to discharge from the PACU. Propensity score for postoperative respiratory dysfunction created. • Pathway creation and prospective pathway implementation: Core group creates pathway guidelines and associated decision support. Build CDS pathway into EMR and collect data following go-live date. 
CDS Pathway:
 
Preoperative Phase

	
1) Physicians/CRNAs will receive an alert identifying the patient as high-risk for postoperative pulmonary complications and the reason for the designation.2) The notification will remind the provider to pick up study sugammadex from the OR pharmacy.3) The notification will display the patient specific lung protective ventilation (LPV) parameters. 
Intraoperative Phase
 
1) There will be a notification reminding the provider to get the study sugammadex.2) If the patient has mechanical ventilation and the parameters are outside the LPV guidelines (5-7cc/kg and at least 5 of PEEP) an alert will pop up with the LPV recommendations.3) If non-depolarizing NMB was given and it has been more than 30 minutes since TOF was documented (and last documentation was <100% and no subsequent NMB was given), then a popup will recommend checking twitches (note we will have the twitch monitor automatically populate into CC).4) Reverse with sugammadex.	
Study Duration	The anticipated duration of subject participation in this study is 1 day (date of surgery).	

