10.0 STUDY ENDPOINTSVariables/Time Points of Interest

- 1) **PACU Discharge Time (primary endpoint):** The duration in minutes from patient arrival in PACU until the ready for discharge order is placed by the anesthesiologist. This captures the time until they are clinically ready for discharge and eliminates noise such as the availability of beds that might effect actual discharge time
- 2) **Incidence of oxygen saturation <90%:** A binary variable indicating if the patient had any oxygen saturations below 90% from arrival in PACU until being marked for discharge
- 3) **Incidence of oxygen saturation <95%:** A binary variable indicating if the patient had any oxygen saturations below 95% from arrival in PACU until being marked for discharge
- 4) **Duration of supplemental oxygen use in PACU:** The total time in minutes that a patient received supplemental oxygen from arrival in PACU until being marked for discharge
- 5) **Reintubation rate:** The incidence of patients who required reinsertion of an endotracheal tube after the patient was extubated in the OR. This includes patients who were reintubated in the PACU or subsequently after PACU discharge.
- 6) **Unplanned Upgrade of Care:** The incidence, defined as a binary variable, of patients who were transferred to an ICU after being admitted to a non-ICU setting.
- 7) **Obstructive Sleep Apnea (OSA):** The presence of obstructive sleep apnea based upon previous structured data in the electronic medical record (EMR) such as prescriptions for CPAP, medical history and the anesthesiologist's preoperative note.

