11.0 STUDY POPULATION

UCLA RRUMC and UCLA Santa Monica patients aged 18 and older who had a general anesthetic with either rocuronium or vecuronium will be considered for inclusion in the study.

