14.0 SUBJECT RECRUITMENT

During the screening phase, patients aged 18 and older who will have a general anesthetic with either rocuronium or vecuronium and who are considered high risk for postoperative pulmonary complications will be flagged in CareConnect and enrolled in the study. Clinicians will receive an alert identifying the patient as a subject in the study and will remind the clinician to pick up the study drug sugammadex from the pharmacy.

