26.0 ESTIMATED SAMPLE SIZE

Sugammadex was introduced into clinical practice at UCLA in May of 2016, thus we have well more than one year of data prior to and after sugammadex introduction. As a result, the power analysis and sample size discussion is roughly the same for the retrospective and prospective portions of this study.

Over the previous one year period, approximately 13,000 patients received general anesthesia with the use of either rocuronium or vecuronium. Given that our surgical volumes are stable we would expect the sample size for the prospective portion of our study to be roughly the same. The table below contains the risk stratification for this group.

To determine the study power, we analyzed the incidence of the primary and secondary outcomes for our historical population. Because there is no current pathway, we are unable to explicitly model the power for performance of identified best practices however the power for the primary outcome as well as secondary outcomes were calculated.

In order to determine our power for the study variables patients were separated into low, medium, and high-risk groups. Low risk patients were those who had no prior documentation of OSA or respiratory disease prior to surgery. Medium risk patients were those with either OSA or respiratory disease and high risk patients were those with both diseases. It is important to note that this classification is significantly simplified as compared to the analysis that will be performed for either the retrospective or prospective studies as it fails to account for key factors such as severity of illness. Nonetheless we believe that these simplifications have the effect of underestimating the potential power and thus the below serves as a conservative estimate.

Table 1. Number of patients in low, medium, and high risk groups from 12/2017- 11/2018	
Risk Class	Number of Patients
Low – No disease	9730
Medium – OSA or Respiratory Disease	2952
High – OSA and Respiratory Disease	445
Total	13,127

Note: The risk classifications above are simplified versions of the true risk classifications to be used in the actual study

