At this point, we estimate that the pathway will recommend sugammadex for all patients in the medium or high-risk groups as well as some patients in the low risk group (i.e. those patients requiring deep neuromuscular blockade to facilitate surgical conditions such as robotic procedures, free flap cases and others). Given the large number of patients, Merck would supply one vial of study drug for each patient. Thus the total amount of study drug would be no more than 6,500 patients for the one year intervention time.

Given 1 year of data, we observed an overall average PACU discharge time of 152.54 minutes (SD=623.86). With one year of post-data, we are adequately powered (90%) to pick up a reduction in PACU discharge time as small as 27.04 (two-sample t-test, alpha=0.025). Since the current difference in PACU discharge time between low and high risk groups is 67.52 (subtracting 216.62-149.10, see table), we feel the 27.04 minimally detectable difference gives us a great chance of detecting a meaningful difference.

Given 1 year of data (pre-period), we observed the rate of patients with any time SpO2<90% was 4.6% (574/12,467). With one year of post-data, we are adequately powered (90%) to pick up a reduction in this rate if it decreases to around 3.7% in the post (chi-square test, alpha=0.025). Since the current difference in patients with any time with SpO2<90% between low and high risk patients is 5.2% (subtracting 9.2%-4.0%), we feel the minimally detectable difference of 3.7% (4.6%-3.8%) is feasible.

Table 2.

	suppl O2, mean (SD)	PACU disch. Time, mean (SD)	Reintubation, freq (%)	Unplanned upgrade, freq (%)	SpO2<90%, freq (%)	SpO2<95%, freq (%)
OVERALL(n=13,277)	74.81 (241.82)	152.54 (623.86)	89 (0.7%)	138 (1.0%)	574 (4.6%)	6510 (52.3%)
low (n=9,841)	74.48 (280.55)	149.10 (599.78)	63 (0.6%)	111 (1.1%)	372 (4.0%)	4603 (50.0%)
medium(n=2,997)	74.98 (95.67)	154.43 (536.58)	23 (0.8%)	22 (0.7%)	164 (5.8%)	1658 (58.8%)
high (n=439)	79.54 (88.44)	216.62 (1321.46)	3 (0.7%)	5 (1.1%)	38 (9.2%)	249 (60.9%)
Smallest detectable difference (90% power)	9.61	24.84	0.4%	0.4%	3.8%	50.3%

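### Secondary Objective 3 concerns high risk patients, but the 9.61-minute detectable difference for supplemental oxygen in Table 2 is a figure for the unselected cohort

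*Combined protocol and SAP*

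**What the plan says.** The third secondary objective in the Protocol Summary (3.0) is "The duration of supplemental oxygen needed by high risk patients before and after intervention". No other primary or secondary objective names a risk group.

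Protocol section 10.0 and the SAP's list of variables define the measurement in identical words, with no mention of risk: "The total time in minutes that a patient received supplemental oxygen from arrival in PACU until being marked for discharge".

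High risk is used in two ways. In section 14.0 it describes the patients the study selects, those "who are considered high risk for postoperative pulmonary complications will be flagged in CareConnect and enrolled in the study". The protocol title and the preoperative alert in section 8.0 use it in the same sense. In section 26.0 it is the top class of a three-level grouping made for the power calculation: "Medium risk patients were those with either OSA or respiratory disease and high risk patients were those with both diseases". That section calls the grouping a considerable simplification of what the analysis will use. The SAP adds that patients will be divided into low, medium and high risk groups for analysis, according to extent of disease.

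Table 2 in section 26.0 gives a single detectable difference for supplemental oxygen: 9.61 minutes at 90% power. The synopsis and section 7.0 put the prospective sample at about 6,500. Section 26.0 limits study drug to no more than 6,500 patients over the intervention year.

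**The concern.** A detectable difference is informative only for the population to be analysed. Table 2 describes a year of unselected cases, essentially the broad pool of section 11.0, where "patients aged 18 and older who had a general anesthetic with either rocuronium or vecuronium will be considered for inclusion". The objective is about a selected subset. Selection changes both the number of patients and the spread of the outcome, and for this outcome the spread differs sharply by class: the SD is 280.55 minutes in the low class, 95.67 in the medium and 88.44 in the high.

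Two things are at stake. A reader of Table 2 is given a precision that was not calculated for the objective. And because this is a before/after comparison on existing records, an analysis population left unstated could be settled after results for several candidate populations are visible.

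**Working it through.** **Inputs.** All from Table 2 (protocol 26.0) unless noted.

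- Overall: n = 13,277, SD 241.82
- Low: n = 9,841, SD 280.55
- Medium: n = 2,997, SD 95.67
- High: n = 439, SD 88.44
- Prospective cohort: about 6,500 (synopsis; section 7.0)
- Power 90%; two-sided alpha 0.05; equal numbers and equal SDs in the two periods

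**Formulas.** Detectable difference = (1.960 + 1.2816) × SD × √(2/n). Power for 9.61 minutes = Φ(9.61 / [SD × √(2/n)] − 1.960).

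**Step 1: reproduce the plan's figure.** 3.2416 × 241.82 × √(2/13,277) = 9.62, against 9.61 stated. At alpha 0.025 the result is 10.46, so the table uses 0.05. The figure is therefore an all-patient one, and 9,841/13,277 = 74% of those patients are in the low class.

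**Step 2: the planned cohort, overall SD.** 3.2416 × 241.82 × √(2/6,500) = 13.7 minutes. Power for 9.61: the standard error is 241.82 × √(2/6,500) = 4.24, and Φ(9.61/4.24 − 1.960) = 62%.

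**Step 3: the planned cohort, assumed mix.** Section 26.0 expects the pathway to recommend sugammadex for all medium and high patients and some low ones. Suppose the 6,500 are the 3,436 medium and high patients plus 6,500 − 3,436 = 3,064 low ones. Then SD ≈ √[(3,064 × 280.55² + 2,997 × 95.67² + 439 × 88.44²)/6,500] ≈ 205, the detectable difference is 11.6 minutes, and power for 9.61 is 76%.

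**Step 4: the simplified classes, for comparison.** High only: 3.2416 × 88.44 × √(2/439) = 19.3. Medium plus high: pooled SD √[(2,997 × 95.67² + 439 × 88.44²)/3,436] = 94.8, and 3.2416 × 94.8 × √(2/3,436) = 7.4.

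| Population | n per period | SD | Detectable difference (min) | Power for 9.61 min |
|---|---|---|---|---|
| All patients (Table 2) | 13,277 | 241.82 | 9.6 | 90% |
| Planned cohort, overall SD | 6,500 | 241.82 | 13.7 | 62% |
| Planned cohort, assumed mix | 6,500 | about 205 | 11.6 | 76% |
| High class of 26.0 | 439 | 88.44 | 19.3 | 36% |
| Medium plus high of 26.0 | 3,436 | 94.8 | 7.4 | 98.8% |

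At alpha 0.025 the last four rows become 14.9, 12.6, 21.0 and 8.1 minutes. The protocol states the 0.025 level for its two primary outcomes, so 0.05 may well be intended here.

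**The case against.** The best defence is that there is little contradiction in the wording. High risk is the study's own label for the patients it flags, so Objective 3 can be read as naming the enrolled cohort. Section 10.0 and the SAP list say how the variable is measured; they do not set an analysis population, and they refer to patients just as generally for the other endpoints. This stands. A reader might infer that the documents prescribe two or three rival analysis sets for this endpoint, but they do not go that far. Some ambiguity remains, because the SAP promises low, medium and high groups for analysis.

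A reader might also infer that the objective means the class where "high risk patients were those with both diseases", and so conclude that the endpoint is badly underpowered at 439 patients, 19.3 minutes and 36% power. The documents do not support that. Section 26.0 expressly calls its classes simplified, the note under Table 1 repeats it, and medium plus high gives a better figure than the one stated.

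It can also be said that section 26.0 expects a prospective sample similar to the historical 13,000, which would suit 9.61. That sentence conflicts with the synopsis and section 7.0, and it describes everyone given the relevant relaxants, not the high risk patients of the objective.

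Finally, Table 2 as a whole rests on the unselected cohort, this is a secondary endpoint, and no sample size is derived from 9.61. All true. These points limit the weight of the finding but do not make 9.61 apply to the objective.

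**Conclusion.** The point holds in a limited form. The 9.61 minutes is correctly calculated, but for all patients, and it does not apply to the high risk population that Objective 3 names. For the planned cohort of about 6,500 per period, the corresponding value is about 11.6 to 13.7 minutes at alpha 0.05. Across the narrower classes of section 26.0 it runs from 7.4 to 19.3 minutes, so the error could go either way and a shortage of power is not shown.

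These values assume equal numbers and SDs in both periods, no loss of patients through matching, and historical SDs that carry over to the flagged patients. The 11.6 also depends on the assumed 3,064 low-class patients. The documents give neither a count nor an SD for patients meeting the actual criteria. Those criteria include BMI, haemoglobin, type of surgery and duration, so the flagged set will contain some patients whom section 26.0 classes as low, where the spread is largest.

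**What to change.** - Name one analysis population for this endpoint, in the same words in Objective 3, section 10.0 and the SAP: patients who meet the high-risk criteria of the synopsis, applied in both periods. Define it by criteria and not by enrolment, because section 13.0 ties enrolment to being supplied study drug, which cannot occur in the baseline year.
- Before that, reconcile sections 12.1 and 6.0 with the synopsis. Both sections list surgery at a study site among the criteria of which one is enough. Read literally, that qualifies every surgical patient at the two sites. The synopsis handles location as an exclusion instead.
- State that the low, medium and high classes of section 26.0 do not define this population.
- Label 9.61 in Table 2 as an all-patient figure and add the detectable difference for the flagged population. Until that set has been counted, show 11.6 and 13.7 minutes for 6,500 per period, and 7.4 and 19.3 minutes for the simplified classes, each with its assumption.

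The cost is wording in a few places, a count from the data warehouse and one added table entry. The stated detectable difference may become less favourable.

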4.0 BACKGROUND AND RATIONALE

Postoperative respiratory dysfunction, as defined by requirements for supplemental oxygen, hypoxia, or (at its' most severe) reintubation is a known potential complication of general anesthesia^{1,2}. Risk factors for this complication include airway surgery, multiple intubation attempts, and patient risk factors such as OSA or preexisting respiratory disease^{3,4}. Previous work at our institution on nearly 23,000 patients in an ambulatory surgery center found that 28.7% of patients had at least one postoperative oxygen saturation less than 95%, and the hypoxia lasted for on average nearly 30 minutes; 1.5% of patients had at least one saturation less than 90%. While the etiology of this complication is multifactorial, one potential contributing factor is continued weakness due to residual neuromuscular blockade⁵.

Neuromuscular blockade is used as part of general anesthesia in order to facilitate endotracheal intubation and help provide optimal surgical conditions⁶. While different classes of these drugs are used in clinical practices, data from our institution indicates that 55% of general anesthetics use rocuronium as a non-depolarizing neuromuscular blocking agent. In order to provide optimal surgical conditions for the duration of the surgery, but still allow for rapid emergence from anesthesia, it is common to use medications which pharmacologically "reverse" the neuromuscular blockade⁷. Traditionally, this was accomplished with neostigmine which serves to block cholinesterase and thereby increase the amount of acetylcholine available at the neuromuscular junction. More recently, sugammadex allows for the direct binding of rocuronium and a direct reversal of effect. This reversal is of faster onset and more effective than the use of neostigmine⁸.

Preliminary data from our institution has shown that morbidly obese patients (which is highly correlated with obstructive sleep apnea) have a prolonged duration of desaturation and increased need for supplemental oxygen as compared to normal weighted controls. For example, the incidence of postoperative oxygen desaturation is 21% in those with a BMI between 18.5 and 25 but more than 40% in those with a BMI between 30 and 45. This results in an odd-ratio of 4.3 for patients with a BMI from 40 to 45 (see attached figure).

In order to facilitate the ability to perform this kind of data analysis, we have developed and maintain the Perioperative Data Warehouse (PDW), a custom-built data warehouse that facilitates the extraction of data from the Epic electronic medical record system (EMR)⁹. To date this infrastructure has been used in the publication of multiple studies in the peer reviewed literature¹⁰⁻¹², and we have been able to demonstrate that the automatic extraction of data from the EMR using this infrastructure is more accurate than manual chart review¹². Querying of our data warehouse has demonstrated that 35.8% of patients who received intraoperative paralysis did not receive reversal of neuromuscular blockade; and, over the past year, of those who received reversal, 57.3% received sugammadex.

Our institution has not only built expertise in the extraction of data from the EMR, but also in the ability to implement effective real time perioperative clinical decision support (CDS). In one study, we have been able to integrate the reporting abilities of the PDW with the CDS capabilities of our EMR in order to provide perioperative reminders to provide adequate postoperative nausea and vomiting (PONV) prophylaxis to high risk patients. This intervention was successful at reducing the overall rate of PONV by 11% and the rate in high risk patients by 20%. Lastly, our department currently has several ERAS pathways that have been implemented. These include pathways for colorectal surgery, cystectomy and donor nephrectomy. In total approximately 300 patients have been involved in these pathways over the past year. We currently maintain automated dashboards that track the outcomes of patients in these pathways using our robust informatics infrastructure.

